7.3 Subgroups

All patients will be analysed together, with no subgroup analyses performed.

7.4 Missing Data

At any timepoint, if there is no data at all for a given outcome, patients with missing data will be excluded from the analysis, and only observed data will be analysed. Missing data will be assumed to be Missing At Random. No imputation procedures will be employed to deal with missing data if it is completely missing at a given timepoint.

During the MTTT, data is collected serially over a short time period. For patients with some data collected, but missing information from the final serial measurements, a Last Observation Carried Forward (LOCF) approach will be used to impute missing data.

[figure not shown]
8 Summary of Study Data

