7.2 Analysis Populations

7.2.1 Full Analysis Population

The Full Analysis Population will consist of patients in the groups to which they were randomised, regardless of deviation from the protocol or whether they received the allocated surgery. Patients with completely missing data at the outcome timepoint will be excluded from this dataset for the particular outcome for which they had missing data.

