9.1 Primary Efficacy Analysis

The primary endpoint of the study is the peak of active GLP-1 concentration at the early mechanistic post-op visit.

The analysis will be performed using Analysis of Covariance (ANCOVA). In the analysis, the peak of active GLP-1 concentration at the early mechanistic post-operative visit will be considered as the outcome measure, whilst baseline peak of active GLP-1 will be included as a covariate.

If the data does not meet the assumptions of the ANCOVA analysis (e.g. normally distributed residuals, homogeneity of variance), a data transformation of the outcome variable (e.g. log transformation) before analysis will be utilised to ensure that the assumptions are met.

The summary statistics for the outcome variable will be produced in accordance with section 8.2. The baseline adjusted difference in outcome values between groups will be reported, along with a corresponding 95% confidence interval.

The primary study analysis will be performed using the Full Analysis Population (see section 7.2.1).

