9.2 Secondary Efficacy Analysis

Secondary outcomes measured on a continuous scale, with a baseline measurement, will be analysed using a similar approach to that outline for the primary efficacy outcome. The data from each post-operative timepoint will be analysed in a separate analysis.

For continuous secondary outcomes where there no baseline measurement, the two groups will be compared using the unpaired t-test. Alternatively, the Mann-Whitney test will be used if the assumptions of the t-test are not met.

For the continuous outcomes, the exceptions to the previously described methods are for the blood, urine and faecal microbial diversity and metabolomics outcomes. These will be analysed using non-metric multidimensional scaling (NMDS) plots. Additionally, PERMANOVA p-values will be generated using the UniFrac weighted distance matrix generated from Mothur. Family-level extended error bar plots will be generated, White's non-parametric t-test with Benjamini-Hochberg FDR will be utilised.

Binary and nominal outcomes (e.g. achieving diabetes remission) will be compared between the two study groups using either the Chi-square test, or Fisher's exact test if the number of responses in some categories is low.

Ordinal outcomes will be analysed using the Mann-Whitney test to allow for the natural ordering of the response categories.

The secondary efficacy analyses will be performed using the Full Analysis Population.

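### A patient with an observed post-operative outcome but a wholly missing pre-operative value is in the Full Analysis Population, yet the no-imputation rule and the baseline-adjusted ANCOVA drop that patient

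*SAP*

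**What the plan says.** Four parts of the SAP bear on this.

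- **Section 7.2.1** defines the Full Analysis Population outcome by outcome: "Patients with completely missing data at the outcome timepoint will be excluded from this dataset". It does not mention a missing pre-operative value.
- **Section 7.4** sets the missing-data rule: "At any timepoint, if there is no data at all for a given outcome, patients with missing data will be excluded from the analysis". It adds: "No imputation procedures will be employed to deal with missing data if it is completely missing at a given timepoint". The one exception is a meal test with some data but "missing information from the final serial measurements, a Last Observation Carried Forward (LOCF) approach will be used to impute missing data".
- **Section 9.1** fits an ANCOVA to the early post-operative peak, and "baseline peak of active GLP-1 will be included as a covariate". It also states: "The primary study analysis will be performed using the Full Analysis Population".
- **Section 9.2** extends the method: "Secondary outcomes measured on a continuous scale, with a baseline measurement, will be analysed using a similar approach".

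Section 8.3 takes baseline as the last measurement before surgery. As far as Table 1 can be read, the meal-test hormones, postprandial glucose, insulin-secretion markers and clamp measures have one pre-operative visit each.

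**The concern.** Consider a patient who has no usable data from the pre-operative meal test, is operated on, and completes the early post-operative test. Section 7.2.1 keeps this patient. The model in 9.1 cannot use the patient without a baseline value, and 7.4, read as worded, forbids supplying one. The primary analysis would then run on a smaller set than the population it names.

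A ban on imputation is defensible for a missing outcome. Applied to a covariate, it discards an observed outcome from a randomised patient. Section 5 plans for 20 evaluable patients per arm, and its 20% allowance is for patients who leave the study. It does not cover patients who stay, give the outcome and are then left out. The gap recurs for each meal-test and clamp outcome analysed by ANCOVA.

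**Working it through.** **1. The rules applied to three patients**

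| Pre-operative meal test | Early post-operative test | 7.2.1 | 7.4 with 9.1 |
|---|---|---|---|
| Complete | Wholly missing | Out | Out |
| Final samples missing | Complete | In | In (LOCF; section 6.4 takes the peak as the maximum) |
| Wholly missing | Complete | In | Out |

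Only the third row conflicts. Section 8.3 offers no fallback for the primary endpoint, because Table 1 shows no second pre-operative GLP-1 measurement.

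**2. The plan's own figure**

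Inputs from section 5: difference 10.0, SD of the change 10.8, level 5%, power 90%, 20 per arm, 20% drop-out.

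n per arm = 2 × (z_alpha + z_power)² × (SD/difference)²

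- One-sided 5%: 2 × (1.645 + 1.282)² × 1.08² = 20.0, so 20.
- Two-sided 5%: 2 × (1.960 + 1.282)² × 1.08² = 24.5, so 25.
- Drop-out: 20 / 0.8 = 25 per arm, 50 in total.

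The stated 20 reproduces one-sided, or two-sided if ANCOVA gains enough: 24.5 × (1 + rho)/2 = 20 gives rho of about 0.63. That question is separate. The work below uses 20 per arm and a two-sided 5% level, in line with the planned 95% interval.

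**3. From change SD to ANCOVA**

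Assume equal SDs before and after surgery, with correlation rho between baseline and outcome:

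- Outcome SD = 10.8 / √(2(1 − rho)): 8.5 at rho 0.2, 9.1 at 0.3, 10.8 at 0.5, 13.9 at 0.7.
- Residual SD = outcome SD × √(1 − rho²) = 10.8 × √((1 + rho)/2).

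**4. Power when patients are dropped or the baseline is filled in**

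Simulated ANCOVA, true difference 10.0, baselines missing completely at random, filled in with the mean of observed baselines over both arms. There were 6,000 runs per setting for rho 0.2 and for 6 missing, and 3,000 otherwise.

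| rho | Missing of 40 | Dropped | Filled in | Gain (points) |
|---|---|---|---|---|
| 0.2 | 4 | 92% | 95% | 3 |
| 0.2 | 6 | 91% | 95% | 4 |
| 0.3 | 2 | 92.8% | 94.0% | 1.2 |
| 0.3 | 4 | 90.5% | 93.2% | 2.7 |
| 0.5 | 2 | 88.5% | 89.5% | 1.0 |
| 0.5 | 4 | 85.6% | 88.4% | 2.8 |
| 0.7 | 2 | 83.5% | 84.1% | 0.6 |
| 0.7 | 4 | 82.8% | 83.7% | 0.9 |
| 0.7 | 6 | 80% | 81% | 1 |

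A repeat with 20,000 runs per setting, covering 2, 4 and 6 missing at all four correlations, gave gains of 0.2 to 4.5 points. In the 3,000-run simulations, mean estimates stayed near 10 under both methods and Type I error lay between 0.043 and 0.058. At a more extreme 8 of 40 missing, power was 86.3% against 92.6% (rho 0.3), 80.2% against 88.0% (rho 0.5) and 75.8% against 79.1% (rho 0.7).

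**5. Why the gain shrinks as rho rises**

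With a fraction f of baselines missing, the large-sample variance ratio (filled in / dropped) is (1 − f) × [(1 − f) + f/(1 − rho²)]. For f = 0.10:

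- rho 0.2: 0.9 × (0.9 + 0.1/0.96) = 0.904
- rho 0.5: 0.9 × (0.9 + 0.1/0.75) = 0.930
- rho 0.7: 0.9 × (0.9 + 0.1/0.51) = 0.986

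The ratio reaches 1 at rho of about 0.73. Above that, simple mean fill-in no longer gains.

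**The case against.** The strongest reply is that 7.2.1 and 7.4 may be one rule. Section 7.4 can be read per outcome and per post-operative timepoint, which matches 7.2.1 and the separate timepoint analyses in 9.2. The wording allows that reading, so I would not call the two sections flatly contradictory. But the SAP then says nothing about a missing covariate, and an ANCOVA routine drops the patient by default. The analysed set still differs from the population named in 9.1.

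It can also be said that 7.4, read widely, does give a rule (observed data only) and that preferring fill-in is a choice of method. That stands in part, and is one reason the point is minor. It does not make 7.2.1 and 9.1 agree.

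The loss is conditional. The SAP gives no expected number of missing baselines. The calculation also starts from 20 per arm, after the full drop-out allowance, when 25 per arm were planned.

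Four stronger readings are tempting and are not supported:

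- **Bias.** None appears when missingness is unrelated to arm. The SAP does not say whether the pre-operative visit precedes randomisation, so the baseline cannot be called a pre-randomisation value. It does precede surgery, in a trial described as double-blinded.
- **A large loss of power.** Taking 10.8 as the SD of the outcome itself gives, at correlation 0.2 with 6 of 40 missing, about 75% against 82%. Section 5 gives 10.8 as the SD of the change. On that basis, power at this correlation stays above 90% even with patients dropped.
- **All secondary outcomes.** The t-test, Mann-Whitney, chi-square and Fisher comparisons need no baseline. Parameters measured more than once before surgery have a fallback in 8.3.
- **Any failed meal test.** A test missing only its final samples is kept.

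**Conclusion.** The point holds as a minor inconsistency with a cheap remedy. A patient with an observed outcome and a wholly missing pre-operative value belongs to the Full Analysis Population under 7.2.1 but is lost from the ANCOVA. This affects the primary endpoint and those continuous secondary outcomes that are analysed by ANCOVA and have one pre-operative measurement.

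The harm is lost precision. Pooled-mean fill-in recovers about 0 to 5 points of power with 2 to 6 of 40 baselines missing at random and a correlation of 0.2 to 0.7. The missing counts, the correlations and the equal SDs before and after surgery are assumptions; the SAP states none of them. The effect is nil if every patient has a baseline.

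**What to change.** Make two changes of wording.

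1. In 7.4, limit the ban on imputation to outcome timepoints.
2. In 9.1 and 9.2, state that a missing pre-operative covariate is replaced by the mean of all observed baselines, pooled over arms and without use of outcome data, or handled by the missing-indicator method. Every patient with an observed outcome is then analysed, as 7.2.1 says. Report the number of baselines filled in for each outcome.

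The cost is about two sentences and one line of code, with no new data. The downside is a simple single imputation of a covariate, which stops gaining precision when baseline and outcome are very strongly correlated. Settling the rule before the data are seen also removes a choice that would otherwise be made at analysis.

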6.4 Derived values

Peak

For each outcome, the peak will be defined as the maximum post-meal concentration (i.e. from time 15 onwards) per patient, regardless of at which timepoint the peak concentration was achieved.

Area Under the curve (AUC)

A number of outcomes from the mixed-meal tests will be summarised by the Area under the curve values. The AUC will be calculated using the trapezium rule.

For outcomes with measurements at time -30, the first value used in the calculation will be the mean of the -30 and 0 timepoints. When there is no -30 value, the time 0 value will be used as the first measurement in the calculation.

Absolute changes from baseline

Absolute changes from baseline will be calculated by subtracting the individual subject's baseline value from the value at the outcome timepoint.

Percentage changes from baseline

Percentage changes from baseline will be calculated by subtracting the individual subject's baseline value from the value at the outcome timepoint, dividing this sum by the baseline value and multiplying by 100.

7 General Considerations

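### Carrying the last meal-test value forward assumes a flat curve: it biases the secondary MMTT AUCs and leaves open a fasting value standing in for the peak

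*SAP*

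**What the plan says.** Section 7.4 treats two situations separately. Where an outcome has no data at all at a visit, the patient is left out of that analysis: "No imputation procedures will be employed to deal with missing data if it is completely missing at a given timepoint". The sentence "Missing data will be assumed to be Missing At Random" belongs to that paragraph. The next paragraph deals with incomplete meal tests. For a patient who has part of the series but is "missing information from the final serial measurements, a Last Observation Carried Forward (LOCF) approach will be used to impute missing data". It sets no minimum number of post-meal samples and makes no distinction between outcomes.

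Section 6.4 then derives the summaries. For AUC, "The AUC will be calculated using the trapezium rule", and where a sample at -30 minutes exists "the first value used in the calculation will be the mean of the -30 and 0 timepoints", so up to two pre-meal samples can be present. For the peak, "the peak will be defined as the maximum post-meal concentration (i.e. from time 15 onwards) per patient". It does not say whether imputed values count.

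Section 7.2.1 states: "Patients with completely missing data at the outcome timepoint will be excluded from this dataset", and applies this outcome by outcome. Section 9.3 allows one sensitivity analysis, of the primary outcome in the per-protocol population, and only if that population differs from the full analysis population.

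**The concern.** Carrying a value forward is reasonable only if the response stays level after the last sample. The SAP's choice of peak as a summary already implies that these responses do not. Section 6.3.2 lists AUCs for active and total GLP-1, PYY, GIP, markers of insulin secretion, glucose, bile acids and FGF-19 and 21, at both the early and the late visit, and section 7.4 applies to all of them. A high value held to the end of the test adds area that was never there. Section 9.2 then analyses the derived AUC as if every sample had been observed, with no allowance for the imputation.

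What is at stake is the between-arm comparison of these secondary AUCs. If tests are cut short more often in one arm, the errors do not cancel. Equal truncation need not cancel either if the curve shapes differ, and the SAP's introduction expects nutrients to reach the distal bowel faster after the long-limb operation.

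The primary endpoint raises a narrower question: what happens to a patient who has fasting samples but no post-meal sample?

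**Working it through.** **Inputs.** From the SAP: the carry-forward rule (7.4), trapezium AUC and maximum from 15 minutes (6.4), target difference 10.0 pmol/L, SD 10.8 pmol/L and 20 patients per arm (section 5). The SAP states no figure for the effect of the rule, so there is none to reproduce. It names only the times -30, 0 and 15 minutes and gives no curve, so the curves below are assumptions.

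**AUC, main assumed curve.** 5, 15, 30, 25, 18, 12, 9, 7 pmol/L at 0, 15, 30, 60, 90, 120, 150, 180 minutes.

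Full AUC = 10×15 + 22.5×15 + 27.5×30 + 21.5×30 + 15×30 + 10.5×30 + 8×30 = 150 + 337.5 + 825 + 645 + 450 + 315 + 240 = 2962.5.

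With carry-forward, AUC = area up to the last sample + last value × minutes remaining:

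| Last sample (min) | AUC with carry-forward | Error |
|---|---|---|
| 150 | 2722.5 + 9×30 = 2992.5 | +1% |
| 120 | 2407.5 + 12×60 = 3127.5 | +6% |
| 90 | 1957.5 + 18×90 = 3577.5 | +21% |
| 60 | 1312.5 + 25×120 = 4312.5 | +46% |
| 30 (peak) | 487.5 + 30×150 = 4987.5 | +68% |
| 15 (rising) | 150 + 15×165 = 2625 | -11% |
| 0 (fasting only) | 5×180 = 900 | -70% |

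**Other assumed curves.** Three further curves at the same times: peak at 15 minutes (5, 30, 26, 16, 10, 8, 6, 5), at 30 minutes (5, 20, 30, 20, 13, 9, 7, 6) and at 60 minutes (5, 9, 18, 25, 20, 14, 10, 7), each run to 120 and to 180 minutes. The error is:
- last sample at the peak: +15% to +122%;
- last sample after the peak: +1% to +95%;
- last sample on the rise: -51% to +36%;
- fasting samples only: -72% to -62%.

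**Effect on an arm mean.** These are errors in one patient's AUC. If all 20 patients in an arm shared the main curve and one was cut short at 60 minutes, the arm mean would rise by (4312.5 - 2962.5)/20 = 67.5, or 67.5/2962.5 = 2.3%. At 90 minutes it would rise by 615/20 = 30.75, or 1.0%; at 120 minutes by 165/20 = 8.25, or 0.3%.

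**Peak.** A carried value equals a value already observed. If any sample from 15 minutes onwards exists, the maximum with carry-forward equals the maximum of the observed post-meal samples. This held for every truncation point on all the curves. Stopping on the rise does understate the true peak (by 28% to 64% on the three further curves, and by 50% on the main curve, 15 against 30), but by the same amount with or without carry-forward.

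Carry-forward changes the peak only when there is no post-meal sample. If the rule is applied then, the fasting 5 becomes the peak in place of 25 to 30, a shortfall of 20 to 25 pmol/L. One such patient moves an unadjusted 20-patient arm mean by 20/20 = 1.0 to 25/20 = 1.25 pmol/L, which is 10% to 12.5% of the 10.0 pmol/L target. The standard error implied by section 5 is 10.8×√(2/20) = 3.4 pmol/L, so 1.25 is about 0.37 of it.

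**The case against.** The strongest defence is that the rule is written for the tail of the test. With only the last one or two samples of the main curve lost, the error is 1% to 6% in that patient's AUC and far less in the arm mean. The large figures need tests abandoned at 30 to 90 minutes, and the SAP does not say that any were. All the affected AUCs are secondary. This stands as a limit on the likely size. It does not rescue the method, because section 7.4 sets no limit on how many samples may be carried.

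A reader might infer three stronger points, which the document does not support:

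- *That the rule distorts the primary peak in general.* It does not, because a carried value cannot exceed the observed maximum. A low peak after early stopping comes from the absence of a minimum-sample rule, and deleting carry-forward would not change it.
- *That a fasting value will be used as the peak.* Section 6.4 speaks of a post-meal concentration. A patient with fasting samples only can fairly be read as having no data for that outcome and so excluded under sections 7.2.1 and 7.4. The other reading is also open, since such a patient has some meal-test data. This is an ambiguity to close, not an established error.
- *That section 7.4 contradicts its own missing-at-random assumption.* That sentence sits with wholly missing outcomes. Missing at random does not justify carry-forward, which needs its own flat-profile assumption that the SAP neither states nor tests, but the two paragraphs do not conflict.

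Nor is it right that AUC is always overstated. The direction depends on where sampling stops.

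**Conclusion.** As written, the rule is wrong for the secondary MMTT AUCs of outcomes that rise and fall. It overstates AUC when sampling stops at or after the peak and can err either way when sampling stops earlier. On the main assumed curve the error in one patient's AUC is +6%, +21% and +46% for a last sample at 120, 90 and 60 minutes. These figures rest on an assumed curve and a 180-minute schedule. The actual bias cannot be derived from the SAP, which gives neither the curve nor the truncation rate, and no planned analysis would reveal it.

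For the primary endpoint the point is one of wording. Carry-forward leaves the peak unchanged once a post-meal sample exists. What remains is that the text does not rule out a carried-forward fasting value as the peak, either at the early post-operative visit or in the baseline peak that serves as the ANCOVA covariate (section 9.1). The plan should be corrected before analysis, but this does not undermine the primary comparison.

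**What to change.** - In section 7.4, replace carry-forward for AUC. Either use a method valid under missing at random (a parsimonious mixed model, or multiple imputation, on the suitably transformed serial values, with AUC derived from the result), or compute AUC over a common observed window. The window option is simpler but changes what the AUC measures, so the window must be fixed in advance.
- In section 6.4, state that imputed values never count towards the peak, and that a test with no observed post-meal sample has a missing peak, at baseline as well as after surgery.
- In section 9.3, add a sensitivity analysis of peak and AUC restricted to complete profiles. Carry-forward may be kept as a sensitivity analysis only.
- Report the number of incomplete meal tests, and the time of the last sample, by arm and visit.

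The cost is SAP wording and modest extra programming, with no new data. If imputation is chosen, the model must be fixed before unblinding and kept small, given about 20 to 25 patients per arm.

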8.1 Subject Disposition

A summary of the number of subjects that reached the various stages of the study will be summarised. Reasons for non-participation and withdrawal will be summarised.

A CONSORT diagram will be produced, such as Figure 1, which will illustrate the flow of patients throughout the study.

Figure 1: Outline CONSORT diagram

8.2 Descriptive Analysis Methods

Continuous variables will be summarised using the number of (non-missing) datapoints, mean and standard deviation if found to follow a normal distribution. Continuous variables not found to be normally distributed will be summarised by the number of datapoints, median and inter-quartile range. Categorical variables will be summarised by the frequency and percentage (based on the non-missing sample size) of values in each category.

8.3 Demographic and Baseline Variables

Baseline values for each parameter are defined as the last value measured before the intervention, i.e. surgery. A summary of patient demographics and baseline measurements are outline in Section 5.4.2.

Descriptive statistics will be produced for these variables for each of the two study arms separately.

The summary statistics will be produced in accordance with section 8.2. No hypothesis tests will be performed to compare the two groups at baseline.

9 Efficacy Analyses

9.1 Primary Efficacy Analysis

The primary endpoint of the study is the peak of active GLP-1 concentration at the early mechanistic post-op visit.

The analysis will be performed using Analysis of Covariance (ANCOVA). In the analysis, the peak of active GLP-1 concentration at the early mechanistic post-operative visit will be considered as the outcome measure, whilst baseline peak of active GLP-1 will be included as a covariate.

If the data does not meet the assumptions of the ANCOVA analysis (e.g. normally distributed residuals, homogeneity of variance), a data transformation of the outcome variable (e.g. log transformation) before analysis will be utilised to ensure that the assumptions are met.

The summary statistics for the outcome variable will be produced in accordance with section 8.2. The baseline adjusted difference in outcome values between groups will be reported, along with a corresponding 95% confidence interval.

The primary study analysis will be performed using the Full Analysis Population (see section 7.2.1).

